10.2.2 Documentation and Notification

These events (SAEs or Serious SARs) must be recorded in the SAE console within OncoreTM for that subject within 24 hours of learning of its occurrence. For multicenter sites, the multicenter Project Manager must be notified via email of all SAEs within 24 hours of learning of its occurrence. SAEs must be recorded on the MedWatch 3500A report form.

10.3 Adverse Event Reporting

10.3.1 IRB Reporting Requirements

UNC:

The UNC IRB will be notified of all SAEs that qualify as an Unanticipated Problem as per the UNC IRB Policies using the IRB's web-based reporting system within 7 days of the Investigator becoming aware of the problem. Please note, these events must be reported to the sponsor within 24 hours of learning of the occurrence.

Multicenter sites:

The UNC IRB will be notified of all SAEs that qualify as an Unanticipated Problem as per the UNC IRB Policies using the IRB's web-based reporting system within 7 days of the Investigator becoming aware of the problem. Please note, these events must be reported to the sponsor within 24 hours of learning of the occurrence.

10.3.2 Pregnancy

Pregnancies and suspected pregnancies (including a positive pregnancy test regardless of age or disease state) of a female subject at UNC or at a multicenter site, occurring while the subject is on study, or within 30 days of the subject's last dose of study product should be recorded as SAEs. The subject is to be discontinued immediately from the study.

For multicenter sites, the pregnancy, suspected pregnancy, or positive pregnancy test must be reported to the Multicenter Project Manager immediately via email ([contact]) or facsimile to [contact]. The female subject should be referred to an obstetrician-gynecologist, preferably one experienced in reproductive toxicity for further evaluation and counseling.

The Investigator will follow the female subject until completion of the pregnancy and must document the outcome of the pregnancy (either normal or abnormal outcome) and report the condition of the fetus or newborn to the Multicenter Project Manager. If the outcome of the pregnancy was abnormal (e.g., spontaneous or therapeutic abortion),

the Investigator should report the abnormal outcome as an AE. If the abnormal outcome meets any of the serious criteria, it must be reported as an SAE.

10.3.3 FDA Expedited Reporting Requirements

A sponsor must report any suspected adverse reaction (SAR) that is both serious and unexpected and related to the cellular product to the FDA. All deaths in the study should be reported expeditiously to FDA regardless of attribution if they occur within 30 days of the infusion of the study cells. Additionally, all grade 4 or greater product infusion reactions, cytokine release syndrome and/or neurologic toxicity must be reported in an expedited fashion. Please refer to section 9.1.2 for the definition of an SAR.

The sponsor must submit each IND safety report on a MedWatch Form 3500A.

Timing

FDA must be notified of potential serious risks within 15 calendar days after the sponsor determines the event requires reporting. FDA must be notified of unexpected fatal or life-threatening suspected adverse reactions as soon as possible but in no case later than 7 calendar days after the sponsor's initial receipt of the information. The sponsor must be notified of the SAE by the investigator within 24 hours of the event. If the results of a sponsor's investigation show that an adverse event not initially determined to be reportable is reportable, the sponsor must report such suspected adverse reaction in an IND safety report as soon as possible, but in no case later than 15 calendar days after the determination is made.

Follow-Up

The sponsor must promptly investigate all safety information it receives. Relevant follow-up information to an IND safety report must be submitted as soon as the information is available and as such the Multicenter Project Manager should be updated within 24 hours of the information becoming available via a follow-up MedWatch Form 3500A.

Notification of Investigators

The sponsor must notify all participating investigators (i.e., all investigators to whom the sponsor is providing cell infusion under its INDs or under any investigator's IND) in an IND safety report of potential serious risks, from clinical trials or any other source, as soon as possible, but in no case later than 15 calendar days after the sponsor determines that the information qualifies for reporting.

Process

If the sponsor deems that an event is both a serious adverse reaction (SAR) AND unexpected, it must also (in addition to OnCore®) be recorded on the MedWatch Form 3500A. Unexpected adverse events or adverse reaction refers to an event or reaction that is not listed in the Investigator's Brochure or is not listed at the specificity or severity that has been observed; or if an investigator's brochure is not required or available, is not consistent with the risk information described in the general investigation plan or elsewhere in the current IND application.

The MedWatch 3500A form and supporting documents defining the event and causality should be sent to the electronic mailbox ([contact]; primary route of submission) (or [contact] (back-up)) of the Multicenter Project Manager along with supporting documentation defining the event and causality.

The MedWatch 3500a form can be accessed at: http://www.fda.gov/Safety/MedWatch/HowToReport/DownloadForms/default.ht m.

Additional Reporting Requirements

The following additional items must be reported via IND safety report:

- *Findings from other studies.* The sponsor must report any findings from epidemiological studies, pooled analysis of multiple studies, or clinical studies, whether or not conducted under an IND, and whether or not conducted by the sponsor, that suggest a significant risk to humans exposed to the cell infusion.
- *Findings from animal or in vitro testing.* The sponsor must report any findings from animal or in vitro testing, whether or not conducted by the sponsor, that suggest a significant risk in humans exposed to the cell infusion, such as reports of mutagenicity, teratogenicity, or carcinogenicity, or reports of significant organ toxicity at or near the expected human exposure.
 - Increased rate of occurrence of serious suspected adverse reactions.
 - All deaths in the study regardless of attribution if they occur within 30 days of the infusion of the study cells.
 - Any product infusion reactions grade ≥ 4 .
 - Any occurrence of cytokine release syndrome (CRS) grade ≥ 4 .

• *Any occurrence of neurotoxicity grade 4.*

Additional Guidance

Please refer to 21CFR312.32 and "Guidance for Industry and Investigators: Safety Reporting Requirements for INDs and BA/BE Studies" for additional information and reporting requirements. All IND Safety Reports will be submitted in accordance with these regulations/guidances.

10.3.4 Institutional Biosafety Committee (IBC)

In addition to the local IRB, any qualifying serious adverse events (SAEs) must be reported to the Institutional Biosafety Committee (IBC). The IBC is responsible for reviewing recombinant DNA research conducted at or sponsored by the institution for compliance with NIH Guidelines as specified in Section III, Experiments covered by the NIH Guidelines and approving those research projects that are found to conform with the NIH Guidelines. As such, the IBC is charged with ensuring compliance with all surveillance, data reporting and adverse event reporting requirements set forth in the NIH Guidelines. The UNC study coordinator will be responsible for notifying the Regulatory Associate within 48 hours should any reportable event occur.

10.4 Data and Safety Monitoring Plan

The Principal Investigator will provide continuous monitoring of subject safety in this trial with periodic reporting to the Data and Safety Monitoring Committee (DSMC). [name] will discuss any DLT event as it occurs, and in consultation with the study statistician, make a decision regarding continued accrual and dose escalation as appropriate. In addition, this triad will evaluate any unexpected toxicities as they occur, and determine if any changes to toxicity monitoring are required.

Meetings/teleconferences will be held with the team at a frequency dependent on study accrual, and in consultation with the study Biostatistician. These meetings will include the investigators as well as study coordinators, data coordinators, regulatory associates, clinical data management associates, and any other relevant personnel the principal investigators may deem appropriate. At these meetings, the research team will discuss all issues relevant to study progress, including enrollment, safety, regulatory, data collection, etc.

The team will produce summaries or minutes of these meetings. These summaries will be available for inspection when requested by any of the regulatory bodies charged with the safety of human subjects and the integrity of data including, but not limited to, the oversight (Office of Human Research Ethics (OHRE) Biomedical IRB, the Oncology Protocol Review Committee (PRC) or the North Carolina TraCS Institute Data and Safety Monitoring Board (DSMB)).

The UNC LCCC Data and Safety Monitoring Committee (DSMC) will review the study on a regular (quarterly to annually) basis, with the frequency of review based on risk and complexity as determined by the UNC Protocol Review Committee. The UNC PI will be responsible for submitting the following information for review: 1) safety and accrual data including the number of subjects treated; 2) significant developments reported in the literature that may affect the safety of participants or the ethics of the study; 3) preliminary response data; and 4) summaries of team meetings that have occurred since the last report. Findings of the DSMC review will be disseminated by memo to the UNC PI, PRC, and the UNC IRB and DSMB.

11.0 STATISTICAL CONSIDERATIONS

11.1 Design, Dose Escalation and MTD

This Phase I dose-escalation trial is designed to evaluate the safety of ATLCAR.CD30 cells. Dose-limiting toxicity is defined in section 4.1.3.3. Dose escalation is guided by the continual reassessment method (CRM) [87] in order to determine the MTD of ATLCAR.CD30 cells. For this study, MTD is defined as the dose that causes DLT in 10% of eligible cases. Three dose levels are being evaluated namely, $2x10^7$ cells/m², $1x10^8$ cells/m², and $2x10^8$ cells/m². Based on our previous trials, we expect a shallow dosetoxicity curve for the doses proposed in this trial. In this trial, CRM is implemented based on one parameter model in O'Quigley et al. [87], with DLT probability at each dose modeled as a_i^b , where constants a are (0.0281, 0.0568, 0.1) and parameter b is being estimated. The prior distribution for b is exponential with mean 1 Subjects are assigned in cohorts of size 2 until the first DLT is observed or the highest dose $2x10^8$ cells/m² is reached without DLT in the first two subjects assigned to $2x10^8$ cells/m² (initial dose escalation). After that assignments are determined by the CRM and subjects are assigned one at a time. Pediatric subjects will not be allowed to enroll at a dose until 2 adult subjects are enrolled and complete their follow-up at that dose level. To reduce the probability of treating subjects at unacceptable toxic dose levels, we employ modifications to the original CRM and do not allow skipping untried doses when the dose is escalated. Subject enrollment starts at the lowest dose level.

Two subjects will initially be allocated to the lowest dose level and followed for 6 weeks post IV injection of ATLCAR.CD30 cells for evaluation of DLTs. If any of the two subjects initially enrolled develop DLTs, the trial will be suspended, and dose levels might be re-evaluated. As soon as the first DLT is observed, dose assignment will be guided by the CRM from that point on. Otherwise, we will continue assigning subjects in cohorts of 2 at escalating doses until either a DLT is observed or the highest dose is reached without a DLT in the first two subjects. After that subjects will be assigned one at a time.

The trial will be suspended, and dose levels re-evaluated as soon as, at the lowest dose, 2 DLTs are observed out of a total of 2 subjects, 3 DLTs out of a total of 3-7 subjects, or 4 DLTs out of more than 7 subjects.

DLTs that occur within 6 weeks after infusion will be factored into the CRM calculations to determine the recommended dose for the subsequent subject. During the study, real-time monitoring of subject toxicity outcome will be performed in order to implement estimation of the dose-toxicity curve and determine dose level for the next subject cohort using one of the pre-specified dose levels. If there is a need to assign a new subject when some of the current subjects are still being followed for DLT, each subject still in follow-up will be temporarily counted as *x* DLTs out of 1, where *x* is the remaining follow-out time fraction. For example, if a subject has been followed for 2 out of 6 weeks, subject will be counted as (1-2/6) = 2/3 of a DLT out of 1 subject. This is a conservative way to account for subjects

still in follow-up. The assignment for a new subject is then determined using the CRM. When the two initial subjects are being followed for DLT at a given dose, additional subjects might be enrolled at a dose prescribed by the CRM using the rule above for imputing temporary DLT for subjects still in follow-up. This applies to pediatric subjects as well as long as there are 2 adult subjects with full 6 week follow-up for DLT at that dose. At the discretion of the investigator pediatric subjects can be assigned to a dose one level lower than specified by the CRM. During the dose escalation part guided by the CRM (after the first DLT is observed), subjects with insufficient cells manufactured and therefore infused with a quantity of cells consistent with a dose lower than the one prescribed by the CRM will be included in the CRM calculations with the weight of 0.5. This will allow us to use data from these subjects and, at the same time, not to bias the dose calculated by the CRM downward. If the number of such subjects exceeds 3, we will consider increasing the sample size of the dose escalation part of the study.

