3.3 Exploratory

This study is a multicenter, open-label phase I clinical trial testing the hypothesis that the administration of ATLCAR.CD30 to subjects with CD30+ lymphoma post autologous transplant is safe as evidenced by the rate of DLT. The rate of DLT will be used to determine the MTD; see section 4.1.3.2. Three dose levels of ATLCAR.CD30 will be evaluated to determine a recommended dose in adult and pediatric subjects. Initially, only adults will be enrolled during the dose escalation phase of the study. Once a dose level has been tested in at least 2 adults without the occurrence of DLTs during the assessment period, children may then be enrolled on that dose level according to the CRM. Each subject will receive one injection followed by close monitoring over the subsequent 6 weeks. See section 7.4 for schedule of longer term follow-up.

Subjects scheduled to undergo an ASCT at one of the protocol sites for treatment of lymphoma will be approached for consent to screening and potential enrollment into LCCC1524-ATL. Peripheral blood cells will be collected from consenting subjects who meet eligibility for cell procurement for creation of ATLCAR.CD30 cells (see section 4.1.1) prior to ASCT. The ASCT, including mobilization and collection of PBSCs, administration of myeloablative therapy, reinfusion of PBSCs and supportive care following transplant will be as per routine standard of care, and not expected to be impacted by enrollment into LCCC1524-ATL. Post ASCT, subjects who meet eligibility criteria for treatment will receive one infusion of ATLCAR.CD30 cells once there is evidence of hematologic recovery as defined in section 4.1.2. Research personnel will keep track of any subjects who undergo procurement but do not undergo treatment with ATLCAR.CD30 cells, and the reason for withholding treatment.

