4.1.3 Dose Escalation Rules

Three dose levels will be evaluated. Using the continual reassessment method (CRM), initial cohort of size two will be enrolled at each dose level (see section 11.), after that subjects are enrolled one at a time until a minimum of 12 subjects is treated. Each subject will receive one injection according to the dosing schedules listed below. We will start with the lowest cell dose $(2 \times 10^7 \text{ cells/m}^2)$ given to subjects in one of our previous trials employing CAR-T cells including the CD28 costimulatory endodomain [26], and we will escalate the cell dose to the highest cell dose $(2 \times 10^8/\text{m}^2)$ given in the same trial [26]. These are also the doses utilized in the phase I trial using ATLCAR.CD30 and described in section 1.5.5. All those

cell doses were safe. A maximum dose is included for each dose cohort in order to avoid excessive dosing secondary to obesity and potentially resulting in toxicity. The maximum dose is calculated based on a body surface area of 2.5 m^2 .

Note: Initially, only adults will be enrolled during the dose escalation phase of the study. Once a dose level has been tested in at least 2 adults without the occurrence of DLTs, children may then be enrolled on that dose level according to the CRM.

Cell dose Levels

Table 1 Group One

Schedule	ATLCAR.CD30 ²	Maximum Dose				
Week 0 Day 11	$2x10^7$ cells/m ²	5x10 ⁷ cells				

Table 2 Group Two

Schedule	ATLCAR.CD30 ²	Maximum Dose				
Week 0 Day 11	$1 x 10^8$ cells/m ²	2.5x10 ⁸ cells				

Table 3 Group Three

Schedule	ATLCAR.CD30 ²	Maximum Dose			
Week 0 Day 11	$2x10^8$ cells/m ²	5x10 ⁸ cells			

The dose is based on the CAR.CD30 expressing cell. With a lower limit of CAR positivity at 15%, even a larger subject (2.0 m^2) would receive 2.66×10^9 total cells which would still be in the lower range of infused cells as reported by Johnson *et al.* [75].

- 1. Only one infusion will be administered, and will be given after stem cell transplantation and engraftment as defined in section 4.1.2.
- 2. If there are insufficient cells manufactured for a subject to receive their proposed dose level, the subject may be infused with a quantity of cells consistent with one of the previously cleared dose levels.

Definition of MTD

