5.0 STUDY POPULATION

Unless otherwise noted, subjects must meet all of the following criteria to participate:

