5.1 Inclusion Criteria for Prior to Cell Procurement

- 1. Informed consent explained to, understood by and signed by subject/guardian; subject/guardian given copy of the procurement/screening informed consent.
- 2. 3 to 17 years of age for pediatric subjects, ≥18 years of age for adults; NOTE: children will not be allowed to enroll in a dose cohort until a minimum of 2 adult subjects were enrolled and complete their DLT assessment follow-up at that dose level.
- 3. Diagnosis of recurrent HL with a treatment plan that will include high dose chemotherapy with/without total body irradiation and autologous cell transplantation.
- 4. NHL subjects with ALK negative CD30+ anaplastic large-cell lymphomas, CD30+ ALCL regardless of ALK status, with chemotherapy-sensitive relapse, CD30+ highrisk DLBCL, CD30+ cutaneous T cell lymphoma, or CD30+ mycosis fungoides who are otherwise eligible for transplant, are eligible for this study.
- 5. Karnofsky or Lansky score of > 60% (APPENDIX III- Lansky and Karnofsky Performance Status)
- 6. Evidence of adequate organ function as defined by:

The following is required prior to procurement (NOTE: labs do not need to be redrawn if they have already been performed as part of SOC pre-transplant work-up; Subject must be eligible to receive ASCT)

- Hgb ≥ 8.0 g/dL
- Bilirubin ≤ 1.5 times the upper limit of normal (ULN)
- AST \leq 3 times ULN
- Serum creatinine ≤ 1.5 times ULN
- Cardiac and pulmonary function that is adequate for ASCT
- 7. In women of child-bearing potential (WOCBP), a negative serum pregnancy test within 72 hours prior to procurement. WOCBP are those who have not been surgically sterilized or have not been free from menses for > 1 year.

8. Considered at high risk for relapse as defined by:

The presence of ≥ 1 of the following: failure to achieve CR post initial treatment; relapsed disease with an initial remission duration of <12 months; or extranodal involvement at the start of pre-transplant salvage therapy.

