12.3 Registration Procedures

All subjects must be registered with the LCCC CPO Multicenter Office at the University of North Carolina before enrollment to study. To register a subject call the Multicenter office at [contact] Monday-Friday 8:30 am – 5:00 pm EST. Scan and email the Multicenter Project Manager ([contact]; preferred) or [contact]) the registration form, signed informed consents, signed eligibility form and all source documents to confirm eligibility. Eligibility may be confirmed by the UNC Study Coordinator for subjects treated at UNC. When sending registration request with eligibility documentation, please allow 24 hours for source to be reviewed.

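### Children may enter a dose after 2 DLT-free adults (4.0, 4.1.3) or after 2 adults with completed follow-up whatever the result (5.1, 5.2, 11.1)

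*Combined protocol and SAP*

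**What the plan says.** Two places make the adults' result part of the condition. The study-plan text of section 4.0 (printed after 3.3 and before 4.1) says that once a dose was tested "in at least 2 adults without the occurrence of DLTs during the assessment period, children may then be enrolled on that dose level". Section 4.1.3 says the same: "Once a dose level has been tested in at least 2 adults without the occurrence of DLTs, children may then be enrolled".

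Four places ask only for completed observation. Criterion 2 of section 5.1 bars children from a dose cohort until "a minimum of 2 adult subjects were enrolled and complete their DLT assessment follow-up at that dose level", and criterion 2 of section 5.2 repeats it. Section 11.1 has "Pediatric subjects will not be allowed to enroll at a dose until 2 adult subjects are enrolled and complete their follow-up" at that level. A later clause of 11.1 allows enrolment while other subjects are still being followed; it "applies to pediatric subjects as well as long as there are 2 adult subjects with full 6 week follow-up for DLT" at that dose. None of the four mentions what the follow-up showed.

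Section 5.0 introduces the criteria with "subjects must meet all of the following criteria to participate", and registration under 12.3 requires a "signed eligibility form and all source documents to confirm eligibility". Section 11.1 adds one pediatric safeguard: "At the discretion of the investigator pediatric subjects can be assigned to a dose one level lower than specified by the CRM".

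**The concern.** The two versions give the same answer unless a DLT leaves fewer than 2 DLT-free adults at the dose. That is the case for which a pediatric gate is written. A site working through 5.1 and 5.2, and a statistician working from 11.1, would find nothing against a child at a dose where 1 of the 2 adults had a DLT. Sections 4.0 and 4.1.3 exclude that child. What is at stake is whether a child may receive a dose that current information puts well above the toxicity target, on the strength of whichever section was consulted.

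**Working it through.** **Inputs (section 11.1).** DLT probability at level i is a_i^b, with a = (0.0281, 0.0568, 0.1). The prior for b is exponential with mean 1 and the target is 10%. The first subjects enter in pairs; after the first DLT, or after the top dose is reached, they enter singly. No untried dose is skipped. The lowest-dose boundary is 2 of 2, 3 of 3–7 or 4 of more than 7. Section 11.2 gives 12 to 18 subjects. The plan does not say whether the DLT rate is estimated by putting the posterior mean of b into a_i^b (plug-in) or by the posterior mean of a_i^b, so both are shown. The plan states no figure on this point to reproduce.

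**Step 1: 1 DLT in 2 adults at level 1.** The posterior is proportional to e^(−b) × a_1^b × (1 − a_1^b), which gives E[b] = 0.342.
- Plug-in estimates for levels 1 to 3: 29.5%, 37.5%, 45.5%.
- Posterior means: 39.0%, 45.4%, 51.8%.
- Posterior probability that the level-1 rate exceeds 10%: 0.887.

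Level 1 is closest to target under both, so if the trial resumes with unchanged dose levels, the next assignment is level 1. Two adults have completed follow-up there and one is DLT-free: 5.1, 5.2 and 11.1 do not bar a child, while 4.0 and 4.1.3 do. The one-level-lower option cannot be used.

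**Step 2: levels 2 and 3.** After 1 of 2 at level 2 or 3 the CRM first moves down. The conflict appears when it returns to that dose.
- Plug-in: returns to level 2 after 4 DLT-free subjects at level 1, and to level 3 after 3 DLT-free subjects at level 2.
- Posterior mean: returns to level 2 after 9 DLT-free subjects at level 1, and to level 3 after 10 (4 at level 1, then 6 at level 2). With the 4 or 6 subjects already treated, that is 13 or 16 subjects, so it cannot happen within 12.

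**Step 3: how often the gates disagree.** A disagreement is a CRM dose with at least 2 completed adults but fewer than 2 DLT-free. Assumptions: adults only up to that point and full follow-up before each assignment. All paths were enumerated exactly; the sums below reproduce the results.

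At the skeleton rates:
- Level 1, exactly 1 of 2: 2 × 0.0281 × 0.9719 = 0.0546.
- Level 2, plug-in: 0.9719² × (2 × 0.0568 × 0.9432) × 0.9719⁴ = 0.9446 × 0.1071 × 0.8922 = 0.0903.
- Level 3, plug-in: 0.9446 × 0.8896 × 0.18 × 0.9432³ = 0.1269.
- Plug-in total with restart: 0.2718. Without restart: 0.2718 − 0.0546 = 0.2172.
- Posterior mean, 18 subjects: 0.0546 + 0.9446 × 0.1071 × 0.9719⁹ + 0.9446 × 0.8896 × 0.18 × 0.9719⁴ × 0.9432⁶ = 0.0546 + 0.0783 + 0.0950 = 0.2279 (0.2280 unrounded).

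| True DLT rates | Estimator | Subjects | With restart after 1 of 2 at level 1 | Without restart |
|---|---|---|---|---|
| Skeleton | Plug-in | 12 or 18 | 27.2% | 21.7% |
| Skeleton | Posterior mean | 12 | 5.5% | 0% |
| Skeleton | Posterior mean | 18 | 22.8% | 17.3% |
| Flat 10% (assumed) | Plug-in | 12 or 18 | 36.2% | 18.2% |
| Flat 10% (assumed) | Posterior mean | 12 | 18.0% | 0% |
| Flat 10% (assumed) | Posterior mean | 18 | 27.8% | 9.8% |

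**Step 4: the stricter rule has two readings.** After 1 of 2 at level 1, reading it as any 2 DLT-free adults opens level 1 once one more adult is DLT-free, 3 adults in total. Reading it as no DLT in the first 2 closes level 1 to children. Level 2 then needs 2 adults. The CRM first moves there at 1 of 11 (plug-in) or 1 of 16 (posterior mean), so it opens at the earliest after 13 or 18 adults, in a trial of 12 to 18.

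**The case against.** The rules do not command opposite things. The weaker texts set minimum conditions and order nobody's enrolment. Section 12.4 requires conduct as described in the whole protocol, so a child must satisfy every condition and the stricter one binds. A reader might infer that the sections cannot be reconciled; they can. What stands is that the criteria and statistical text used at enrolment do not carry the stricter condition.

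Other controls exist. A DLT in the first lowest-dose pair suspends the trial. Section 10.4 requires a decision on accrual after every DLT, taken with the statistician. Registration is reviewed centrally and every infusion takes place at the lead site. These limit the risk, but none states a pediatric criterion.

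The frequencies depend on assumptions. The two 12-subject posterior-mean figures come entirely from an assumed restart and fall to 0% without it. On the reading that any 2 DLT-free adults suffice, each conflict ends with the next DLT-free adult at that dose. It would be wrong to infer that up to 27.2% of such trials would wrongly dose a child, because the documents give no number or share of children.

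The high estimates in step 1 also apply to adults, and requiring 2 DLT-free adults alone would admit a child at 1 of 3 at level 1, where the estimate is still 21.8% (plug-in) or 29.9% (posterior mean). That objection is sound, and the fix therefore adds a review step.

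A reader might also infer that nothing is written for resuming after 1 DLT in the first lowest-dose pair. The documents do not support that: 11.1 gives the next dose by the CRM and 10.4 provides the accrual decision. Only a criterion for lifting the suspension is absent. That is missing detail and forms no part of this point.

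**Conclusion.** The concern holds as an inconsistency in a safety rule for children. Sections 4.0 and 4.1.3 carry the protective condition; 5.1, 5.2 and both clauses of 11.1 leave it out, and these are the texts applied at enrolment and dose assignment. At the skeleton rates the chance that the gates disagree at some assignment is 5.5% to 27.2% with a restart after 1 of 2 at level 1, and 0% to 21.7% without one. The spread reflects the unnamed estimator and the final sample size. These are chances of disagreement between two rules under the assumptions in step 3, not of harm to a child. The level-1 case is the most serious, because the estimate is about three to four times the target and no lower dose exists, but it requires a deliberate decision to resume. The text should be corrected; the design and sample size are unaffected.

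**What to change.** Use one sentence in section 4.0, section 4.1.3, criterion 2 of 5.1, criterion 2 of 5.2 and both clauses of 11.1:

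*Children may be enrolled at a dose level only after at least 2 adults at that level have each completed the 6-week DLT follow-up without a DLT; if another adult at that level had a DLT, the section 10.4 review must also agree before a child is enrolled there.*

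This keeps the protection already written in 4.0 and 4.1.3 and settles which reading applies. It avoids the reading that could close the trial to children until 13 to 18 adults are treated, and it makes admission at, say, 1 of 3 an explicit decision. The existing suspension rule stays as it is.

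The change is to protocol wording, with no added subjects or procedures. Its downside is that the first child at a dose where an adult had a DLT may wait for about one further adult's follow-up.

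### Section 11.1 lets the CRM give an adult the next untried dose before the pair below has finished its 6-week DLT window

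*Combined protocol and SAP*

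**What the plan says.** Section 11.1 first describes an initial escalation. "Two subjects will initially be allocated to the lowest dose level and followed for 6 weeks post IV injection". If no DLT occurs, "Otherwise, we will continue assigning subjects in cohorts of 2 at escalating doses until either a DLT is observed"; the other stopping point is a DLT-free first pair at the top level. The CRM takes over, one subject at a time, after that. A later sentence in 11.1 likewise places the CRM-guided part after the first DLT. Section 4.1.3 agrees: an "initial cohort of size two will be enrolled at each dose level (see section 11.), after that subjects are enrolled one at a time".

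Section 11.1 also covers subjects who arrive while others are pending. Each pending subject is counted as a DLT fraction equal to the share of follow-up still to come. While the first two subjects at a dose are in that state, "additional subjects might be enrolled at a dose prescribed by the CRM using the rule above". Two restrictions stand nearby. The modified CRM does "do not allow skipping untried doses when the dose is escalated", and pediatric subjects may use this route only "as long as there are 2 adult subjects with full 6 week follow-up for DLT at that dose".

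**The concern.** The two descriptions give different answers to the same question: what dose may an adult receive when the first pair at a level is DLT-free but has not completed 6 weeks? Under the pair scheme, the next level is closed. Under the overflow sentence, the CRM decides, although no DLT has occurred and the top dose has not been cleared. The no-skipping rule does not settle it, because moving up to the adjacent untried level skips nothing. The completed-pair condition does not settle it for adults.

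The step from level 1 to level 2 is five-fold (2×10^7 to 1×10^8 cells/m²), in what Section 1.6 calls the first human use of these cells after ASCT. Two statisticians following 11.1 could assign different doses to the same patient. The question is whether the fractional-DLT rule is strict enough to keep the next level closed anyway.

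**Working it through.** **Inputs from Section 11.1.** "MTD is defined as the dose that causes DLT in 10% of eligible cases", so the target is 0.10. The DLT probability at level i is a_i^b, where "constants a are (0.0281, 0.0568, 0.1) and parameter b is being estimated"; b has an exponential prior with mean 1. A subject followed t of 6 weeks without DLT counts as x = 1 − t/6 of a DLT. The plan's example reproduces: t = 2 gives 1 − 2/6 = 2/3.

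**Method.** Each subject contributes a_i^(bx) × (1 − a_i^b)^(1−x) to the likelihood. The posterior for b is obtained by numerical integration. The dose chosen is the one with estimated DLT probability closest to 0.10, at most one level above the highest dose tried. The plan does not name the point estimator, so four were run: posterior mean of b plugged in, posterior median of b plugged in, posterior mean of the DLT rate itself, and posterior mode of b. Let s be the summed remaining fraction of the pair.

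**Most of the window.** Level-1 pair infused on the same day, posterior-mean plug-in:

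| Week | Estimated DLT rate, levels 1 / 2 / 3 | Dose |
|---|---|---|
| 2 | 0.411 / 0.489 / 0.563 | 1 |
| 4 | 0.183 / 0.256 / 0.335 | 1 |
| 5 | 0.080 / 0.132 / 0.197 | 1 |

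The fractional rule holds the dose here, as the plan intends.

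**When the next level opens.** The day is 42(1 − s/2) for a same-day pair, or 42(1 − s) for the second subject when the first is complete, rounded up.

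| Estimator | Level 2 opens at | Days | Level 3 opens at (level 1 complete at 0/2) | Days |
|---|---|---|---|---|
| Posterior-mean plug-in | s ≤ 0.314 | 36 / 29 | s ≤ 0.389 | 34 / 26 |
| Posterior-median plug-in | s ≤ 0.187 | 39 / 35 | s ≤ 0.248 | 37 / 32 |
| Posterior mean DLT rate | not early | – | s ≤ 0.050 | 41 / 40 |
| Posterior mode | not early | – | not early | – |

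For the first row, 42(1 − 0.314/2) = 35.4 and 42(1 − 0.314) = 28.8; 42(1 − 0.389/2) = 33.8 and 42(1 − 0.389) = 25.7. With the same estimator, s = 0.30 at level 1 gives 0.071 / 0.120 / 0.182, so level 2 is closest to 0.10. At level 2, s = 0.38 gives 0.039 / 0.073 / 0.123, so level 3 is closest. With the posterior mean DLT rate, even a completed 0/2 at level 1 gives 0.085 / 0.117 / 0.157, so the CRM stays at level 1.

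**Chance of a hidden DLT.** Assume DLT times are uniform over 6 weeks. A subject who is DLT-free with remaining fraction f and true DLT probability p still has one ahead with probability pf / (1 − p(1 − f)). At the posterior-mean plug-in thresholds, with one subject pending:

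- Level-1 pair, p = 0.0281, f = 0.314: 0.00882 / 0.98072 = 0.9%.
- Level-2 pair, p = 0.0568, f = 0.389: 0.02210 / 0.96530 = 2.3%.
- p = 0.10, f = 0.314: 0.0314 / 0.9314 = 3.4%.
- p = 0.10, f = 0.389: 0.0389 / 0.9389 = 4.1%.

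**How many subjects.** A newly infused subject counts as a full DLT. After one level-2 assignment on day 36 (same-day pair, s = 0.286), the posterior-mean plug-in gives 0.253 / 0.332 / 0.413. After one level-3 assignment on day 34 (s = 0.381), it gives 0.136 / 0.202 / 0.276. Both send the next subject to level 1, so about one subject per level is exposed.

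**The case against.** The overflow sentence can be read as a deliberate exception to the pair scheme: the authors foresaw patients arriving mid-window, set a time-weighted rule and described it as conservative. Section 4.1.3 defers to Section 11. Saying that a pair is followed for 6 weeks does not say that nobody else may be dosed meanwhile. This is a fair reading, but it leaves unsaid whether the exception may open an untried level, and it does not fit the statements in 11.1 that place the CRM after the initial escalation.

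The points about size largely stand. Early opening depends on an unnamed estimator; the five-fold step to level 2 stays closed under the posterior mean DLT rate and the posterior mode. Uniform DLT timing probably overstates the hidden risk: Section 1.5.2 puts CRS onset at days to weeks after infusion, and Section 8.3 describes related cells expanding for only 2–3 weeks. The documents give no distribution of DLT times, so the reduction cannot be quantified. The same three dose levels were given to nine subjects without attributable adverse events or CRS (Section 1.5.5), though without conditioning and outside transplant. Section 10.4 provides ongoing safety monitoring, but its case-by-case escalation decision is triggered by a DLT, so it supplies no rule for this situation.

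**Conclusion.** The concern holds. Section 11.1 gives two incompatible rules for assigning adults while an initial pair is pending, and no text bars the next untried dose.

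The gap is narrow. Under the posterior-mean plug-in it covers the last 6 to 8 days for a same-day pair, and the last 13 to 16 days of the second subject's window when the first is complete. It is shorter under the median plug-in, 1–2 days at level 3 only under the posterior mean DLT rate, and absent under the mode. The day counts rest on the plan's model, prior and imputation rule plus the choice of estimator; the hidden-DLT percentages add the uniform-timing assumption. It should be corrected because it lies in the dose-assignment rule for the primary objective and is cheap to close.

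**What to change.** Add to Section 11.1:

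> During initial dose escalation, subjects enrolled while the first pair at a dose is pending are assigned by the CRM only among dose levels already tried. No untried level opens until both initial subjects at the level below have completed 6 weeks without DLT.

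Also name the CRM point estimator: posterior-mean plug-in, posterior-median plug-in, or posterior mean DLT rate. The two sentences close the gap whichever is chosen.

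The cost is that a third subject may wait up to about two weeks or receive a dose already tried. Infusion generally falls 14 to 20 days after the stem cells are returned (Section 4.1.2), and a wait could take a subject past that period, so the already-tried dose is the likelier outcome.
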